### **2.2 Endpoints/Outcome Measures**

Aim 1: Focus groups will uncover knowledge and awareness of prostate cancer; understanding of genetic testing; perceptions of genetic testing; risks and benefits of testing

Aim 2: Outcome will be the design of a feasible intervention to employ in a community-practice setting.

Aim 3: Analysis of intervention data will determine: extent of decisional conflict; knowledge of prostate cancer and genetic testing for prostate cancer risk; individual assessment of prostate cancer risk; intentions to seek genetic testing (if appropriate)

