### Treatment Assignment Procedures

#### 3.3.1 Randomization Procedures

Aim 2/3: At the time of consent and enrollment into the study, each participant will be randomly assigned to participate in the intervention arm or the control arm. A randomization scheme will be provided by the study biostatistician.

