**Study Randomization and Informed Consent.** Those who are eligible to participate will be randomized to either the intervention or the control arm. Men randomized to the intervention arm will be scheduled to attend a health education session hosted at CityLife Clinic or virtually, while men who are randomized to the control arm will receive educational materials about PCA genetic testing in the mail or in person. All men who agree to participate will be read a consent statement over the phone or in person and will verbally agree to consent to participate. A copy of the consent statement will be provided to them for their records.

**Baseline Survey.** All participants will complete a brief baseline questionnaire over the telephone or in person with the study manager. Items to be assessed at baseline include knowledge about prostate cancer, their personal family cancer history, knowledge of genetic testing and screening, attitudes towards genetic testing, subjective norms about genetic testing, decisional conflict about genetic testing, and intentions to seek genetic counseling. Knowledge about PCA genetics and genetic testing will be measured using a 14-item scale, recently published by the study team in a population of men undergoing genetic testing. The measure for decisional conflict will be the SURE Decisional Conflict Scale, a low-literacy validated measure to screen for decisional conflict. The four questions encompass the following with Yes/No responses: (1) Do you feel sure about the best choice for you? (2) Do you know the benefits and risks of your options? (3) Are you clear about which benefits and risks matter most to you? (4) Do you have enough support and advice to make a choice? Demographic data related to age, race/ethnicity, family history of prostate or other cancer, and other pertinent health information will be collected.

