### **Study Intervention.**

*Intervention Arm:* Men who are randomized to the intervention arm will be invited to a peer health education session, either in-person or virtually. Eighty-eight of the 176 men will be randomized to this group, and we will host sessions that attract roughly 6-8 men at a session. Our previous experience conducting peer health education sessions found that 6-8 men was an ideal attendance level, as it allowed for interaction and discussion but did not feel overwhelming. Each session will be facilitated by two peer educators, who can share responsibilities and interact with each other. We expect to offer 12-15 sessions, or roughly 1-2 sessions per month. Sessions will be scheduled at various times of the day and days of the week, to accommodate men with varying schedules and commitments. Each peer educator will be compensated for 2 hours of time to run a session from start to finish, being compensated at \$20/hour.

First, the peer educator will introduce the topic of PCA, so that men understand the disease and how it relates to their health. The educator will lead a discussion regarding PCA risk, family history, PCA genetics, considerations of genetic testing, implications of genetic testing on family and self, and financial and ethical considerations. The discussion is meant to be interactive, with men sharing stories and experiences and peer educators answering questions and clarifying facts. All information will be delivered in a culturally appropriate manner by peer educators who are from the community they are serving. Immediately following the discussion, men will complete a post-survey to measure short-term changes knowledge about prostate cancer and genetic testing, thoughts about cancer, in decisional conflict about genetic testing, attitudes toward genetic testing, subjective norms about testing, and intentions to seek genetic testing. We will also get feedback on the peer-led session.

*Control Arm:* After providing informed consent and completing the baseline survey over the telephone or in-person, eighty-eight men will be randomized to this arm and each man will receive an educational booklet. It is expected that materials will be mailed within 24 hours of the

---

telephone call or provided to the participant in person. The information will cover PCA risk, family history, PCA genetics, considerations of genetic testing, implications of genetic testing on family, and financial and insurance considerations.

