**Endpoint Survey.** All men, regardless of study arm, will complete an endpoint survey. A member of the study team will call each participant two months after either attending a peer education session (intervention arm) or being mailed the educational print materials (control arm). Previous research shows that two months is an adequate amount of time to digest the material and act upon it, if desired. The majority of items on the baseline survey, except for the demographic information, will be repeated on the endpoint survey. Participants who are not reached by telephone will be contacted by mail and by email to attempt to retain the maximum number of participants over time.

**Participant Compensation.** Each man who participates in all study-related activities will receive \$50 over the course of the study. Men in the intervention group will receive \$25 for completing the baseline survey via the mail and \$25 for completing the endpoint survey over the telephone at two-months post-intervention. Men in the control group will receive \$25 in their mailed packet of materials after completion the baseline survey and an additional \$25 for completing the endpoint survey over the telephone at two-months post-intervention.

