**Referral to Genetic Counseling.** Men from both groups who decide they want to proceed with genetic counseling and genetic testing will be given the number to contact the Cancer Risk and Genetics Program at Sidney Kimmel Cancer Center at Jefferson, led by [name] (study PI). Once men contact the Genetics Program, an intake will be performed to determine if they meet personal or family history criteria for genetic testing. Current NCCN criteria for PCA genetic testing include any of the following: (1) personal history of advanced or metastatic PCA, (2) family history of brother, father, or multiple family members diagnosed with PCA at age <60, (3) first-degree, second-degree, or third-degree relatives with cancers of the breast, ovary, prostate, pancreas, colon, or endometrium suggestive of a hereditary cancer syndrome. Men will then be scheduled for a genetic counseling visit to formally cover information regarding genetic testing such as how cancers can be inherited, types of genetic test results, and implications for the man and his family. Once the man agrees to proceed with testing, a saliva sample will be collected and sent to Invitae, a CLIA-certified and experienced clinical genetic testing laboratory to perform multigene testing. Genes to be tested by sequencing and deletion/duplication testing will include *BRCA1*, *BRCA2*, *ATM*, *PALB2*, *CHEK2*, *NBN*, the DNA mismatch repair genes, and additional genes as needed. Invitae follows ACMGG guidelines for variant classification and all standard procedures for variant reclassification updates. Since men in this study may be underinsured, the study will pay for the cost of genetic testing for all men who undergo genetic counseling. Once

---

results return, men will be called to come in for a results disclosure visit to discuss their results and answer any questions.

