## 9.2 Analysis Plans

**Decisional Conflict to Consider Genetic Testing.** All study variables, such as demographics, PCA knowledge, and outcome responses, will be summarized in tables with descriptive statistics or graphically in data plots at each time they are assessed along with changes in responses over time. We will investigate imbalances in these data for potential confounding of primary and exploratory endpoint analyses and investigate disparities and intervention effect modification in various subgroups of subjects. The primary outcome is decisional conflict regarding genetic testing assessed by the 4-item SURE scale. To compute a summary decisional conflict score, the Likert-scaled responses will be averaged across the SURE item responses provided by a subject completing at least 2 of the 4 questions. The change in decisional conflict scores between baseline and endpoint at 2-months will be calculated and group means for these changes compared between subjects randomized to receive control materials vs. those randomized to receive the peer health education intervention (i.e., by intention to treat). The significance of the difference will be evaluated at the 0.05 level using a two-sided Student's t-test. The assumptions for this test will be carefully evaluated. If the changes are substantially skewed, they will be summarized with group medians and evaluated for significant differences by the nonparametric Wilcoxon's rank sum test. If concerns arise over potential confounding from imbalances in baseline covariates, we will conduct a sensitivity analysis by applying analysis of covariance (ANCOVA) to adjust the comparison for baseline imbalances, including baseline decisional conflict scores.

**Descriptive and Exploratory Analyses.** Exploratory analyses will include estimating the proportion of AA men meeting the NCCN guidelines for genetic testing and computing a 95% confidence interval using the Clopper-Pearson exact method. Summary statistics and qualitative analyses will be used to assess the genetic counseling experience of those subjects accepting the offer for genetic counseling. Additional analyses will include estimating the intervention effect on genetic testing/counseling intentions and uptake, respectively, changes in attitudes toward genetic testing, and understanding of personal genetic test results using discrete variable tests, such as McNemar's test.

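### Minor (exploratory analyses only): the sole test named for the intervention effect on intentions and uptake is McNemar's, a paired within-person test that cannot give a between-arm effect

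*Combined protocol and SAP*

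**What the plan says.** Section 9.2 (Descriptive and Exploratory Analyses) lists among its additional analyses "estimating the intervention effect on genetic testing/counseling intentions and uptake, respectively". The same sentence continues to attitudes and to understanding of test results, and ends with the methods: "uptake, respectively, changes in attitudes toward genetic testing, and understanding of personal genetic test results using discrete variable tests, such as McNemar's test". No other test or model is named for these outcomes anywhere in the document. The t-test, the Wilcoxon rank sum test and ANCOVA in Section 9.2 are all tied to the decisional conflict score.

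The design is individually randomised with two parallel arms. Section 3.3.1 states that "each participant will be randomly assigned to participate in the intervention arm or the control arm", and nothing pairs a man in one arm with a man in the other.

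The outcomes are collected at different times:

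- **Intentions** are on the baseline survey, and Section 6 (Endpoint Survey) says "The majority of items on the baseline survey, except for the demographic information, will be repeated on the endpoint survey". Section 2.2 lists intentions among the Aim 3 measures.
- **Uptake** arises only through the later referral: "Men from both groups who decide they want to proceed with genetic counseling and genetic testing will be given the number to contact" the genetics program (Section 6, Referral to Genetic Counseling).
- **Understanding of personal results** is surveyed once, at the post-test visit (Section 6, Assessment of genetic counseling experience).

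**The concern.** An intervention effect in a randomised trial is a contrast between arms. McNemar's test takes two binary responses from the same person and asks whether changes in one direction outnumber changes in the other. Arm does not enter it.

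For uptake and understanding of results, the before-and-after table it needs does not exist. For intentions the table may exist, but the test then answers whether men changed over two months, not whether peer education changed them more than the booklet did. Section 6 gives both arms education on largely the same topics, so some shift common to both arms is plausible. A within-arm result reported as the intervention effect would credit that common shift to peer education.

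The stake is limited to the exploratory results on intentions and uptake.

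**Working it through.** The plan gives no rates, sample size or power for these outcomes, so there is no figure of its own to reproduce. All counts and rates below are assumptions. The arm sizes are from Section 9.3: 75 per arm for analysis and 88 per arm randomised.

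**1. Which outcomes can be paired**

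| Outcome | Baseline value? | Can McNemar's be formed? | Does it contain an arm contrast? |
|---|---|---|---|
| Intentions | Yes | Yes, within arm, if the item is binary and repeated | No |
| Changes in attitudes | Yes | Yes, within arm, if dichotomised | No |
| Uptake | No | No | - |
| Understanding of results | No | No | - |

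**2. One example for intentions.** In each arm of 75, let 12 men move from no to yes and 3 from yes to no.

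- Exact McNemar within one arm, 15 discordant pairs: p = 2 x [C(15,0) + C(15,1) + C(15,2) + C(15,3)] / 2^15 = 2 x (1 + 15 + 105 + 455) / 32,768 = 1,152 / 32,768 = 0.035.
- Net change per arm: (12 - 3)/75 = 0.12. Difference between arms: 0.12 - 0.12 = 0.
- Variance of one man's change: 15/75 - 0.12^2 = 0.1856.
- SE of the arm difference: sqrt(2 x 0.1856/75) = 0.0704. The 95% CI is 0 +/- 1.96 x 0.0704, or -13.8 to +13.8 points.

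The same data give a nominally significant paired test in the intervention arm and an arm difference of exactly zero.

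**3. How often this would happen.** With 75 men, treat the numbers gaining and losing as multinomial and sum the probability of all outcomes with exact McNemar p <= 0.05. The true shift is identical in both arms.

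| Gain / lose | Within-arm McNemar significant |
|---|---|
| 10% / 5% | 12.3% |
| 12% / 6% | 15.6% |
| 20% / 10% | 27.6% |
| 16% / 4% | 58.0% |

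Logistic regression of the two-month response on arm and baseline response was simulated under the same four settings (8,000 trials each, baseline intention 30% or 50%). It found an arm effect in 4.6% to 5.0% of trials. The percentages in the table are not type I error rates: a real within-arm shift exists, and McNemar's test is right to detect it. The two methods answer different questions.

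**4. What a direct estimate for uptake would look like.** Newcombe's interval combines the Wilson limits (l, u) of each arm. The lower limit is d - sqrt[(p1 - l1)^2 + (u2 - p2)^2] and the upper limit is d + sqrt[(u1 - p1)^2 + (p2 - l2)^2]. For 22 v 10 of 88:

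- p1 = 0.250, Wilson 0.171 to 0.350; p2 = 0.114, Wilson 0.063 to 0.197; d = 12/88 = 0.136.
- Lower: 0.136 - sqrt(0.0787^2 + 0.0830^2) = 0.022. Upper: 0.136 + sqrt(0.0996^2 + 0.0507^2) = 0.248.

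In points, other assumed counts give: 9 v 4, 5.7 (-2.4 to 14.2); 18 v 10, 9.1 (-1.8 to 19.9); 30 v 18, 13.6 (0.5 to 26.2). These show the precision of the proposed analysis, not harm from the plan. They treat men as independent, although the intervention is delivered in group sessions of about 6 to 8.

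**The case against.** The strongest defence is that the sentence names an open class of tests with one example. It covers four outcomes, and for changes in attitudes a paired test is a reasonable description of within-arm change. The surrounding text also points towards comparing arms: the hypothesis in Section 9.1 is between arms, the primary analysis compares randomised groups, and the sentence itself speaks of an intervention effect. The analyses are exploratory, where less detail is normal. All of this stands. What remains is that the only example given cannot address the two outcomes listed first, and no method that can is named for them.

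Three stronger readings are tempting and should not be drawn:

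- **That the plan will use McNemar's test as its between-arm test.** The document does not say so, and for uptake it would be impossible.
- **That the false-positive rate is 12% to 58%.** Those figures are rejection rates for a true within-arm change under assumed rates.
- **That the intention question differs between baseline and follow-up.** The baseline description has "decisional conflict about genetic testing, and intentions to seek genetic counseling", while a later one has "subjective norms about testing, and intentions to seek genetic testing". But the latter describes the survey given straight after the session, in the intervention arm only, not the two-month survey. The Endpoint Survey text excepts only demographics by name, Section 9.2 itself joins testing and counselling intentions, and the instruments are not in the document. A mismatch cannot be established.

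**Conclusion.** The point holds as a minor one. For the promised intervention effect on intentions and uptake, the plan names a single test. That test has no arm contrast, and it cannot be computed for uptake or for understanding of results. This rests on the text and the design alone and is secure.

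The possible harm is conditional. Only if McNemar's test were used for intentions, and read as the effect, would shared change be mistaken for an effect of peer education. The worked example shows that this can happen with an arm difference of zero, but its size depends entirely on assumed counts. The primary analysis and the sample size are not affected.

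**What to change.** Replace the sentence in Section 9.2 with outcome-specific methods:

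- **Uptake:** the between-arm risk difference with a 95% CI (for example Newcombe) and one pre-named test, chi-square or Fisher. Analyse all randomised men by assigned arm, over the same stated time window in both arms. State whether uptake means counselling, testing or each separately.
- **Intentions:** the two-month response modelled on arm, adjusted for the baseline response, by logistic or ordinal regression according to the item's scale. If no matching baseline item exists, compare the two-month response between arms unadjusted, which randomisation still supports.
- **McNemar's test:** within-arm change only, labelled as such.
- **Understanding of results:** descriptive, among tested men, because they are a subset formed after randomisation.

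Other between-arm methods would also serve; what matters is that one is named. The cost is a few sentences of SAP wording and slightly more analysis, with no additional participants.

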## 9.3 Sample Size Considerations

**Sample Size Considerations and Missing Data Analysis.** In a study conducted at Jefferson of 273 older AA subjects at risk of PCA, the SURE decisional conflict instrument showed good reliability (Cronbach's  $\alpha = 0.76$ ) and the summary scores were  $3.77 \pm 0.76$ , on average. A sample size of  $n=75$  per group ( $N=150$  total) is necessary in order to have at least 90% power to detect a difference of at least 0.40 Likert scale units (a moderate, but clinically important, relative effect size of about  $\frac{1}{2}$  standard deviation) in mean decision conflict between control and intervention by

a two-sided t-test with a 5% type I error rate. We plan to over-recruit to 176 men (88 men per arm) to account for ~15% expected attrition. Missing data patterns across all efficacy outcome variables over time will be evaluated and multiple imputation will be considered if the data appear likely to be missing at random. Sensitivity to missing data mechanism assumptions will be evaluated, with methods such as pattern mixture modeling, if more than 10% of data are missing for any outcome variable.

## 10 Source Documents and Access to Source Data/Documents

Study staff will maintain appropriate medical and research records for this study, in compliance with ICH E6, and regulatory and institutional requirements for the protection of confidentiality of participant information. Study staff will permit authorized representatives of SKCC and regulatory agencies to examine (and when required by applicable law, to copy) research records for the purposes of quality assurance reviews, audits, and evaluation of the study safety, progress and data validity.

## 11 Quality Control and Quality Assurance

Prior to the start of the study, a manual of operating procedures will be created to describe all study-related tasks and procedures. The study PI will be responsible for ensuring that all study staff are trained on the manual and are competent in executing study procedures.

In addition to ensuring that all study staff are trained on study procedures, it is important that the peer health educators are familiar and competent in delivering the experimental arm of the study intervention. To assess peer educator competency prior to the start of the intervention, we will adapt evaluation materials from the International Society of Nurses in Genetics 2011 Consensus Panel and survey on knowledge and understanding of PCA genetics and genetic results. Example true/false assessment questions will include: (1) Factors such as personal behavior (diet, exercise) and environmental conditions (exposures) can raise the risk of getting prostate cancer; (2) Men with a family history of prostate cancer should also consider other factors that could raise the risk of getting prostate cancer, such as diet or exposures; (3) A family history of prostate cancer can raise the risk of getting prostate cancer; (4) Family history of additional cancers, such as breast cancer, can raise the risk of getting prostate cancer; (5) Having a history of prostate cancer on his mother's side of the family, can raise the risk of a man getting prostate cancer; (6) A genetic test can tell if someone will definitely get prostate cancer in the future; (7) Genetic testing may still be important even if a man has prostate cancer; (8) Patients with one cancer can be at risk for getting other cancers if the patient has a genetic mutation.

Additional multiple-choice questions will include: (1) What types of genetic test results can you get from genetic testing? (2) How can genetic testing be used in treatment of prostate cancer? (3) How can genetic testing be used in prostate cancer screening discussions? (4) What should a man know about genetic discrimination laws before proceeding with genetic testing? (5) What additional cancer risks might be learned from genetic testing for prostate cancer? Peer health educators will be expected to score correctly on 80% or more of the questions to proceed with the intervention in Aim 3. Any areas of deficiency in understanding will be addressed by the study team in a group format or one-on-one with a peer health educator.

